## **2. STUDY OBJECTIVES AND ENDPOINTS**

To evaluate the safety and efficacy of lebrikizumab compared with placebo in patients with moderate-to-severe AD.

### **2.1. Primary Endpoint**

For FDA:

The primary efficacy endpoint is the percentage of patients with an IGA score of 0 or 1 and a reduction  $\geq 2$  points from Baseline to Week 16.

For EMA:

Co-primary endpoints will be used as follows:

- Percentage of patients with an IGA score of 0 or 1 and a reduction  $\geq 2$  points from baseline to Week 16.
- Percentage of patients achieving EASI-75 ( $\geq 75\%$  reduction from Baseline in EASI score) at Week 16

## 2.2. Secondary Endpoints

**Table 1: Secondary Endpoints**

FDA	EMA

 
• Percentage of patients achieving EASI-75 (<math>\geq 75\%</math> reduction from Baseline in EASI score) at Week 16
 
• Percentage of patients achieving EASI-90 (<math>\geq 90\%</math> reduction from Baseline in EASI score) at Week 16
 
• Percentage change in Pruritus Numerical Rating Scale (NRS) score from Baseline to Week 16
 
• Percentage of patients with a Pruritus NRS of <math>\geq 4</math>-points at Baseline who achieve a <math>\geq 4</math>-point reduction from Baseline to Week 16
 
• Percentage change in EASI score from Baseline to Week 16
 
• Change from Baseline to Week 16 in percent BSA
 
• Percentage of patients achieving EASI-90 at Week 4
 
• Percentage change in Sleep-loss score from Baseline to Week 16
 
• Change from Baseline in Sleep-loss score at Week 16
 
• Percentage of patients with a Pruritus NRS of <math>\geq 4</math>-points at Baseline who achieve a <math>\geq 4</math>-point reduction from Baseline to Week 4
 
• Percentage of patients with a Pruritus NRS of <math>\geq 4</math>-points at Baseline who achieve a <math>\geq 4</math>-point reduction from Baseline to Week 2
 
• Percentage of patients with a Pruritus NRS of <math>\geq 4</math>-points at Baseline who achieve a <math>\geq 4</math>-point reduction from Baseline to Week 1
 
	
 
• Percentage of patients achieving EASI-90 (<math>\geq 90\%</math> reduction from Baseline in EASI score) at Week 16
 
• Percentage change in Pruritus Numerical Rating Scale (NRS) score from Baseline to Week 16
 
• Percentage of patients with a Pruritus NRS of <math>\geq 5</math>-points at Baseline who achieve a <math>\geq 4</math>-point reduction from Baseline to Week 16
 
• Percentage of patients with a Pruritus NRS of <math>\geq 4</math>-points at Baseline who achieve a <math>\geq 4</math>-point reduction from Baseline to Week 16
 
• Percentage change in EASI score from Baseline to Week 16
 
• Percentage of patients achieving EASI-90 at Week 4
 
• Change from baseline in DLQI at Week 16
 
• Percentage of patients achieving <math>\geq 4</math>-point improvement in DLQI from baseline to Week 16
 
• Percentage change in Sleep-loss score from Baseline to Week 16
 
• Change from Baseline in Sleep-loss score at Week 16
 
• Percentage of patients with a Pruritus NRS of <math>\geq 5</math>-points at Baseline who achieve a <math>\geq 4</math>-point reduction from Baseline to Weeks 1, 2 and 4
 
• Percentage of patients with a Pruritus NRS of <math>\geq 4</math>-points at Baseline who achieve a <math>\geq 4</math>-point reduction from Baseline to Weeks 1, 2 and 4
 


**Table 1: Secondary Endpoints (Continued)**

FDA	EMA

Specific for Maintenance Period:
 
 
Percentage of patients from those re-randomized having achieved EASI-75 at Week 16 who continue to exhibit EASI-75 at Week 52 (EASI-75 calculated relative to baseline EASI score)
 
Percentage of patients from those re-randomized having achieved IGA 0 or 1 and a <math>\geq 2</math>-point improvement from Baseline at Week 16 who continue to exhibit an IGA 0 or 1 and a <math>\geq 2</math>-point improvement from Baseline at Week 52
 
	
Specific for Maintenance Period:
 
 
Percentage of patients from those re-randomized having achieved EASI-75 at Week 16 who continue to exhibit EASI-75 at Week 52 (EASI-75 calculated relative to baseline EASI score)
 
Percentage of patients from those re-randomized having achieved IGA 0 or 1 and a <math>\geq 2</math>-point improvement from Baseline at Week 16 who continue to exhibit an IGA 0 or 1 and a <math>\geq 2</math>-point improvement from Baseline at Week 52
 
Percentage of patients from those with a Pruritus NRS of <math>\geq 4</math>-points at baseline re-randomized having achieved <math>\geq 4</math>-point reduction from baseline at Week 16 who continue to exhibit <math>\geq 4</math>-point reduction from baseline at Week 52
 
Percentage of patients from those with a Pruritus NRS of <math>\geq 5</math>-points at baseline re-randomized having achieved <math>\geq 4</math>-point reduction from baseline at Week 16 who continue to exhibit <math>\geq 4</math>-point reduction from baseline at Week 52
 
Percentage change in SCORAD (having achieved EASI-75 at Week 16) from baseline at Week 52
 

Evaluate the pharmacokinetics of lebrikizumab.
 
 
Average serum lebrikizumab concentration
 
	
Evaluate the pharmacokinetics of lebrikizumab.
 
 
Average serum lebrikizumab concentration
 

### 2.3. Other Secondary Endpoints

- Proportion of patients with EASI-75, EASI-90 and EASI-50 by visit
- Proportion of patients with IGA Score of 0 or 1 and a reduction  $\geq 2$  points from Baseline by visit
- Percentage change from Baseline in EASI Score by visit
- Percentage change from Baseline in Pruritus NRS by visit
- Percentage of patients with Pruritus NRS change of  $\geq 4$  from Baseline by visit
- Percentage of patients with a Pruritus NRS score of  $\geq 4$  points at Baseline who achieve a  $\geq 4$ -point reduction from Baseline by visit
- Change from Baseline in Sleep-Loss score by visit
- Change from Baseline in DLQI/CDLQI by visit
- Change from Baseline in EQ5D by visit

- Change from Baseline in POEM by visit
- Change from Baseline in PROMIS Anxiety measure by visit
- Change from Baseline in PROMIS Depression measure by visit
- Change in ACQ-5 score from Baseline to Week 16 in patients who have self-reported comorbid asthma
- Percentage change from Baseline to Week 16 in SCORAD

### 3. STUDY DESIGN

This is a randomized, double-blind, placebo-controlled, parallel-group study which is 52 weeks in duration. The study is designed to confirm the safety and efficacy of lebrikizumab as monotherapy for moderate-to-severe atopic dermatitis utilizing a 16-week induction treatment period and a 36-week maintenance treatment period (Figure 1).

Eligible adult and adolescent ( $\geq 12$  to  $< 18$  years weighing  $\geq 40$  kg) patients with moderate-to-severe AD for at least one year, defined according to the American Academy of Dermatology Consensus Criteria, an EASI Score of  $\geq 16$ , an IGA score of  $\geq 3$  and a BSA of  $\geq 10\%$  will be enrolled.

During the 16-week Induction Period, approximately 400 patients will be stratified and randomized 2:1 to either 250 mg lebrikizumab (loading dose of 500 mg given at Baseline and Week 2) or placebo by SC injection Q2W. All study drug injections will be administered in the clinic.

After completion of the Week 16 visit, patients who have responded to treatment [defined as having an IGA of 0 or 1 or a 75% reduction in EASI from Baseline to Week 16 (EASI-75)] will enter the Maintenance Period and will be re-randomized 2:2:1 to one of the following treatment groups: lebrikizumab 250 mg Q2W, lebrikizumab 250 mg Q4W, or placebo Q2W. Patients will be instructed to self-administer study drug at home.

Patients who do not achieve an IGA of 0 or 1 or an EASI-75 at Week 16 and those patients not maintaining an EASI-50 response following re-randomization at Week 24, 32, 40 or 48 will be assigned to an Escape Arm and receive lebrikizumab 250 mg as open-label treatment Q2W through Week 52. Patients not achieving an EASI-50 response after 8 weeks of treatment in the Escape Arm will be terminated from the study.

Efficacy will be measured through the IGA, EASI, BSA, SCORAD, Pruritus and Sleep-loss scores.

Safety will be assessed by monitoring adverse events, serum chemistry, hematology and urinalysis laboratory testing, physical examination, pulse and blood pressure. An independent Data Safety Monitoring Board will monitor patient safety by conducting formal reviews of accumulated safety data periodically throughout the trial. Additionally, adolescents will be monitored for hormones.

Quality of life and impact of disease will be assessed using the POEM, DLQI/CDLQI, EQ-5D and PROMIS Anxiety and Depression measures. Patients reporting comorbid asthma at study entry will complete the ACQ-5.

Serum samples will be collected for pharmacokinetic analysis and immunogenicity.

Photographs of a selected target lesion will be obtained in a subset of patients participating in this study.

Patients completing this 52-week study will be offered the option of continued treatment in a separate long-term extension study (DRM06-AD07).

[figure not shown]
Patients who early terminate or choose not to enter the long-term extension study will undergo a follow up visit approximately 12 weeks after the last study drug injection for safety follow-up.

A patient is considered to have completed the study if he/she has completed the last scheduled visit:

- For subjects continuing into LTE, upon completion of week 52 visit and rolling into LTE study
- For subjects not continuing into LTE, when subject had either week 52 or ETV, and safety follow up visit (12 weeks after last IP administration)

The end of the study is defined as the date of the last visit of the last patient in the study shown in the Schedule of Visits and Procedures.

**Figure 1: Study Schema**

\* Responder is defined as having an IGA of 0 or 1 or a 75% reduction in EASI from Baseline to Week 16 (EASI-75)

### 3.1. Duration of the Study

The total duration of a patient's participation in this study will be approximately 66 weeks (Screening: maximum duration of 30 days; Induction Period: 16 weeks; Maintenance Period: 36 weeks; Follow Up: 12 weeks from last dose at Week 50).

### 3.2. Study Population and Number of Patients

Approximately 400 patients with moderate to severe atopic dermatitis, including approximately 50 adolescent patients ( $\geq 12$  to  $< 18$  years, weighing  $\geq 40$  kg).

## 4. SELECTION OF PATIENTS

Prospective approval of protocol deviations to recruitment and enrollment criteria, also known as protocol waivers or exemptions, is not permitted.

### 4.1. Inclusion Criteria

Patients must meet all the following criteria to be eligible for this study:

1. Adults and adolescents ( $\geq 12$  to  $< 18$  years of age and weighing  $\geq 40$  kg).
2. Chronic AD (according to American Academy of Dermatology Consensus Criteria) that has been present for  $\geq 1$  year before the screening visit.
3. Eczema Area and Severity Index (EASI) score  $\geq 16$  at the baseline visit.
4. Investigator Global Assessment (IGA) score  $\geq 3$  (scale of 0 to 4) at the baseline visit (see Section 8.2.1).
5.  $\geq 10\%$  body surface area (BSA) of AD involvement at the baseline visit.
6. History of inadequate response to treatment with topical medications; or determination that topical treatments are otherwise medically inadvisable.
7. Apply a stable dose of non-medicated topical moisturizer at least twice daily for  $\geq 7$  days prior to the baseline visit.
8. Completed electronic diary entries for pruritus and sleep-loss for a minimum of 4 of 7 days preceding randomization.
9. Willing and able to comply with all clinic visits and study-related procedures and questionnaires.
10. For women of childbearing potential: agree to remain abstinent (refrain from heterosexual intercourse) or use a highly effective contraceptive method during the treatment period and for at least 18 weeks after the last dose of lebrikizumab or placebo.

NOTE: A woman of childbearing potential (WOCBP) is defined as a postmenarcheal female, who has not reached a postmenopausal state ( $\geq 12$  continuous months of amenorrhea with no identified cause other than menopause) and has not undergone surgical sterilization (removal of ovaries and/or uterus).

NOTE: The following are highly effective contraceptive methods: combined (estrogen and progestogen containing) hormonal contraception (oral, intravaginal, transdermal) associated with inhibition of ovulation, progestogen-only hormonal contraception (oral, injectable, implantable) associated with inhibition of ovulation, intrauterine device (IUD), intrauterine hormone-releasing system (IUS), bilateral tubal occlusion, vasectomized partner, or sexual abstinence. The reliability of sexual abstinence should be evaluated in relation to the duration of the clinical trial and the preferred and usual lifestyle of the patient. Periodic abstinence (e.g., calendar, ovulation, symptothermal, or postovulation methods) and withdrawal are not acceptable methods of contraception.

11. Male patients must agree to use an effective barrier method of contraception during the study and for a minimum of 18 weeks following the last dose of study drug if sexually active with a female of child bearing potential.
12. Provide signed informed consent/assent as described in Section 10.2.

## 4.2. Exclusion Criteria

Patients meeting any of the criteria below will be excluded from this study:

1. Participation in a prior lebrikizumab clinical study.
2. History of anaphylaxis as defined by the Sampson criteria (Sampson, 2006).
3. Treatment with topical corticosteroids, calcineurin inhibitors or phosphodiesterase-4 inhibitors such as crisaborole within 1 week prior to the baseline visit.
4. Prior treatment with dupilumab or tralokinumab.
5. Treatment with any of the following agents within 4 weeks prior to the baseline visit:
  - a. Immunosuppressive/immunomodulating drugs (e.g., systemic corticosteroids, cyclosporine, mycophenolate-mofetil, IFN- $\gamma$ , Janus kinase inhibitors, azathioprine, methotrexate, etc.)
  - b. Phototherapy and photochemotherapy (PUVA) for AD.
6. Treatment with the following prior to the baseline visit:
  - a. An investigational drug within 8 weeks or within 5 half-lives (if known), whichever is longer.
  - b. B Cell-depleting biologics, including rituximab, within 6 months.
  - c. Other biologics within 5 half-lives (if known) or 16 weeks, whichever is longer.
7. Use of prescription moisturizers within 7 days of the baseline visit.
8. Regular use (more than 2 visits per week) of a tanning booth/parlor within 4 weeks of the screening visit.
9. Treatment with a live (attenuated) vaccine within 12 weeks of the baseline visit or planned during the study.
10. Uncontrolled chronic disease that might require bursts of oral corticosteroids, e.g., co-morbid severe uncontrolled asthma (defined by an ACQ-5 score  $\geq 1.5$  or a history of  $\geq 2$  asthma exacerbations within the last 12 months requiring systemic [oral and/or parenteral] corticosteroid treatment or hospitalization for  $> 24$  hours).
11. Active chronic or acute infection requiring treatment with systemic antibiotics, antivirals, antiparasitics, antiprotozoals, or antifungals within 2 weeks before the baseline visit, or superficial skin infections within 1 week before the baseline visit.  
NOTE: patients may be rescreened after infection resolves.
12. Evidence of active acute or chronic hepatitis (as defined by the Department of Health & Human Services Centers for Disease Control and Prevention) or known liver cirrhosis.
13. Diagnosed active endoparasitic infections or at high risk of these infections.

14. Known or suspected history of immunosuppression, including history of invasive opportunistic infections (e.g., tuberculosis [TB], histoplasmosis, listeriosis, coccidioidomycosis, pneumocystosis, and aspergillosis) despite infection resolution: or unusually frequent, recurrent, or prolonged infections, per the Investigator's judgment.
15. History of human immunodeficiency virus (HIV) infection or positive HIV serology at screening.
16. In the Investigator's opinion, any clinically significant laboratory results from the chemistry, hematology or urinalysis tests obtained at the screening visit.
17. Presence of skin comorbidities that may interfere with study assessments.
18. History of malignancy, including mycosis fungoides, within 5 years before the screening visit, except completely treated in situ carcinoma of the cervix, completely treated and resolved non-metastatic squamous or basal cell carcinoma of the skin.
19. Severe concomitant illness(es) that in the Investigator's judgment would adversely affect the patient's participation in the study. Any other medical or psychological condition that in the opinion of the Investigator may suggest a new and/or insufficiently understood disease, may present an unreasonable risk to the study patient because of his/her participation in this clinical trial, may make patient's participation unreliable, or may interfere with study assessments.
20. Pregnant or breastfeeding women, or women planning to become pregnant or breastfeed during the study.

## **5. STUDY DRUG**

### **5.1. Investigational Medicinal Product**

Lebrikizumab is a sterile liquid solution containing 125 mg/mL lebrikizumab, histidine acetate, sucrose, polysorbate 20, and sterile water for injection, USP, pH 5.4–6.0. Placebo solution is identical in appearance and content to the active solution except for lebrikizumab. All study drug (lebrikizumab and placebo) will be supplied as a sterile pre-filled syringe with a pre-assembled needle safety device (PFS-NSD). Each pre-filled syringe is intended for a single 2 mL dose (250 mg) administered subcutaneously (SC).

### **5.2. Storage and Labeling**

Study drug is to be stored under refrigerated conditions (2–8°C) and protected from excessive light and heat. Study drug should not be frozen, shaken or stored at room temperature. Temperature excursions outside of 2–8°C must be reported to the Sponsor or the designee. Clinical trial material will be labeled according to country's regulatory requirements.

### **5.3. Patient Randomization**

Patients will be assigned a unique identifier by the sponsor. Any patient records, datasets or tissue samples that are transferred to the sponsor will contain the identifier only; patient names or any information which would make the patient identifiable will not be transferred. All patients

will be randomly allocated to receive the study treatment using an electronic data capture system at the Baseline visit. The allocation to treatment will be prospectively stratified by geographic region (US versus EU versus rest of world), age (adolescent patients 12 to <18 years versus adults  $\geq$ 18 years) and disease severity (IGA 3 versus 4). At the Baseline visit (Day 1), once a patient is considered eligible to participate in the study, demographic and stratification information will be entered into the EDC system to receive a medication number assigning a kit to a patient.

During the Maintenance Period, the EDC will be used to re-randomize a patient to a maintenance treatment based on the IGA or EASI score at Week 16.

### **5.3.1. Induction Period (Day 1 to Week 16)**

Patients will be randomized 2:1 to one of the following treatment groups:

- Lebrikizumab 250 mg Q2W: 500 mg lebrikizumab administered at Baseline and Week 2 (loading dose; two PFS-NSD) and 250 mg Q2W through Week 14
- Placebo: 4 mL (two PFS-NSD) administered at Baseline and Week 2 and 2 mL Q2W through Week 14

### **5.3.2. Maintenance Period (Week 16 to Week 52)**

After completion of the Week 16 visit, patients who have responded to treatment [defined as having an IGA score of 0 or 1 or, at least a 75% reduction in EASI from Baseline to Week 16 (EASI-75)] will be re-randomized 2:2:1 to one of the following treatment groups:

- Lebrikizumab 250 mg Q2W: 250 mg lebrikizumab given every 2 weeks through Week 50
- Lebrikizumab 250 mg Q4W: 250 mg lebrikizumab given every 4 weeks through Week 50
- Placebo: placebo given every 2 weeks

Responders who received placebo during the first 16 weeks of the study and who are re-randomized to lebrikizumab arms will receive a loading dose of lebrikizumab of either 500 mg given at Week 16 or 500 mg given at Weeks 16 and 18, based on the active treatment group assigned in Maintenance. To maintain study blinding, all patients re-randomized in the Maintenance period will receive the same number of injections at all visits throughout the Maintenance Period using an appropriate combination of active and placebo injections ([Table 2](#)).

**Table 2: Maintenance Period Dosing Schedule by Treatment Group**

Induction Treatment Assignment	Maintenance Treatment Assignment	Maintenance Loading Dose	Week 20, 24, 28, 32, 36, 40, 44, 48	Week 22, 26, 30, 34, 38, 42, 46, 50
Active	Lebrikizumab 250 mg Q2W	Week 16: one active and one placebo injection Week 18: one active and one placebo injection	One active injection	One active injection
	Lebrikizumab 250 mg Q4W	Week 16: one active and one placebo injection Week 18: two placebo injections	One active injection	One placebo injection
	Placebo	Week 16: two placebo injections Week 18: two placebo injections	One placebo injection	One placebo injection
Placebo	Lebrikizumab 250 mg Q2W	Week 16: two active injections Week 18: two active injections	One active injection	One active injection
	Lebrikizumab 250 mg Q4W	Week 16: two active injections Week 18 two placebo injections	One active injection	One placebo injection
	Placebo	Week 16: two placebo injections Week 18: two placebo injections	One placebo injection	One placebo injection

**5.3.3. Escape Arm**

Patients who require topical or systemic rescue treatment (Section 6.3) for atopic dermatitis during the Induction Period, or, are non-responders at Week 16, will be eligible for treatment in an Escape Arm where patients will receive lebrikizumab Q2W from Week 16 through Week 52. In addition, patients who do not maintain an acceptable response during the Maintenance Period (have an EASI score <50% of baseline), will be eligible for the Escape Arm.

To enter the Escape Arm, patients must have been compliant with study visits during the Induction Period or the Maintenance Period, respectively. Patients receiving systemic rescue medication (Section 6.3) will be required to washout for 5 half-lives prior to initiating treatment in the Escape Arm. All patients eligible for the Escape Arm will receive blinded loading doses, based on their prior treatment assignment (see Table 3 below), followed by 250 mg lebrikizumab Q2W through Week 52 on study in an open-label fashion. Patients in the Escape Arm must

comply with study visits every 4 weeks. Patients in the Escape Arm, not achieving or maintaining an EASI50 score after 8 weeks of treatment will be terminated from the trial.

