**Study Design:**

This is a randomized, double-blind, placebo-controlled, parallel-group study which is 52 weeks in duration. The study is designed to confirm the safety and efficacy of lebrikizumab as monotherapy for moderate-to-severe atopic dermatitis utilizing a 16-week induction treatment period and a 36-week long-term maintenance treatment period.

Eligible adult and adolescent ( $\geq 12$  to  $< 18$  years weighing  $\geq 40$  kg) patients with moderate-to-severe atopic dermatitis for at least one year, defined according to the American Academy of Dermatology Consensus Criteria, an Eczema Area and Severity Index Score (EASI) of  $\geq 16$ , an Investigator Global Assessment (IGA) score of  $\geq 3$  and a body surface area (BSA) of  $\geq 10\%$  will be enrolled.

During the 16-week Induction Period, approximately 400 patients will be stratified and randomized 2:1 to either 250 mg lebrikizumab (loading dose of 500 mg given at Baseline and Week 2) or placebo by subcutaneous (SC) injection every 2 weeks (Q2W). All study drug injections will be administered in the clinic.

After completion of the Week 16 visit, patients who have responded to treatment [defined as having an IGA of 0 or 1 or a 75% reduction in EASI from Baseline to Week 16 (EASI-75)] will enter the Maintenance Period and will be re-randomized 2:2:1 to one of the following treatment groups: lebrikizumab 250 mg Q2W, lebrikizumab 250 mg given every four weeks (Q4W), or placebo Q2W. Patients will be instructed to self-administer study drug at home.

Responders who received placebo during the first 16 weeks of the study and who are re-randomized to lebrikizumab arms will receive a loading dose of lebrikizumab of either 500 mg given at Week 16 or 500 mg given at Weeks 16 and 18, based on the active treatment group assigned in Maintenance.

Patients who do not achieve an IGA of 0 or 1 or an EASI-75 at Week 16, and those patients not maintaining an EASI-50 response following re-randomization at Week 24, 32, 40 or 48, will be assigned to an Escape Arm and receive lebrikizumab 250 mg as long-term treatment Q2W through Week 52. Patients not achieving an EASI-50 response after 8 weeks of treatment in the Escape Arm will be terminated from the study.

Efficacy will be measured through the IGA, EASI, BSA, SCORAD, Pruritus and Sleep-loss scores.

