**Table 3: Escape Arm Dosing Schedule by Treatment Group**

Induction Group Assignment	Maintenance Treatment Assignment	Maintenance Loading Dose (Blinded)	Week 20 to 50 (Unblinded: 250mg Q2W)
Patients entering Escape Arm at Week 16			
Active	Escape arm	Week 16: one active and one placebo injection Week 18: one active and one placebo injection	One active injection
Placebo	Escape arm	Week 16: two active injections Week 18: two active injections	One active injection
Patients entering Escape Arm at Week 24, 32, 40 and 48			
	Lebrikizumab 250 mg Q2W	At entry: one active and one placebo injection At next administration: one active and one placebo injection	One active injection
	Lebrikizumab 250 mg Q4W	At entry: one active and one placebo injection At next administration: one active and one placebo injection	One active injection
	Placebo	At entry: two active injections At next administration: two active injections	One active injection

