**8.2.2. Eczema Area and Severity Index (EASI)**

The EASI is used to assess the severity and extent of AD; it is a composite index with scores ranging from 0 to 72, with the higher values indicating more severe and/or extensive disease. Assessors must be trained and certified by the Sponsor prior to conducting this assessment.

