5.1.3.2. Maintenance Escape Period

[figure not shown]
Patients who do not achieve an IGA of 0 or 1 or an EASI-75 at Week 16, patients received topical or systemic rescue therapy between baseline to Week 16 and those patients not maintaining an EASI-50 response following re-randomization at Week 24, 32, 40, or 48 will be

assigned to an Escape Arm and receive lebrikizumab 250 mg as open-label treatment Q2W through Week 52. Patients not achieving an EASI-50 response in the Escape Arm after 8 weeks of treatment will be terminated from the study.

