Maintenance W16 Escape Population	Including patients who were NOT re-randomized to Lebrikizumab 250 mg Q2W, Lebrikizumab 250 mg Q4W or placebo but assigned to escape arm at Week 16, and received at least one dose of study treatment during the maintenance period. Selective efficacy analyses for the maintenance period will be conducted on the Maintenance W16 Escape Population.
Maintenance W24-48 Escape Population	Including patients from Maintenance Primary and Secondary Population who escaped to Lebrikizumab 250 mg Q2W due to EASI-50 non-response at Week 24, 32, 40 or 48. Selective efficacy analyses for the maintenance period will be conducted on the Maintenance W24-48 Escape Population
All Lebrikizumab Safety Population	All randomized patients who received at least 1 dose of lebrikizumab treatment during Combined Induction and Maintenance Periods. Safety analyses for the Combined Induction and Maintenance Periods will be conducted on All Lebrikizumab Safety Population. Selective safety analyses for the Combined Induction and Maintenance Periods plus the follow-up Period will be conducted on All Lebrikizumab Safety Population.

Abbreviations: EASI = Eczema Area and Severity Index; IGA = Investigator Global Assessment;

Table KGAB.6.2. Treatment Groups and Comparisons for Each Study Period and Analysis Population

Study Period	Analysis Population	Treatment Groups	Abbreviation	Inferential Comparisons When Applicable
Induction Period	ITT; Safety	Placebo; Lebrikizumab 250 mg Q2W	PBO; LEB250Q2W	LEB250Q2W vs PBO
Maintenance Blinded Period	Maintenance Primary Population	Lebrikizumab_Res/Placebo; Lebrikizumab_Res/Lebrikizumab 250 mg Q4W; Lebrikizumab_Res/Lebrikizumab 250 mg Q2W; Total Lebrikizumab_Res/ Lebrikizumab (Safety analysis only)	LEB_Res/PBO; LEB_Res/LEB250Q4W; LEB_Res/LEB250Q2W; Total LEB_Res/LEB (Safety analysis only)	LEB_Res/LEB250Q4W vs LEB_Res/PBO; LEB_Res/LEB250Q2W vs LEB_Res/PBO
Maintenance Blinded Period	Maintenance Secondary Population	Placebo_Res/Placebo; Placebo_Res/Lebrikizumab 250 mg Q4W; Placebo_Res/Lebrikizumab 250 mg Q2W	PBO_Res/PBO; PBO_Res/LEB250Q4W; PBO_Res/LEB250Q2W	No Between-Group or Overall Comparisons
Maintenance Escape Period	Maintenance W16 Escape Population	Lebrikizumab_NonResp/ Lebrikizumab 250 mg Q2W; Placebo_NonResp/Lebrikizumab 250 Q2W	LEB_NonResp/ LEB250Q2W; PBO_NonResp/ LEB250Q2W	No Between-Group or Overall Comparisons

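### The EASI cut-off for maintenance escape in Protocol 5.3.3 points the wrong way: it describes patients who still respond

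*Protocol*

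**What the plan says.** Protocol Section 5.3.3 sets eligibility for the Escape Arm. For entry from the Maintenance Period it admits "patients who do not maintain an acceptable response during the Maintenance Period (have an EASI score <50% of baseline"). The same section later ends participation for Escape Arm patients "not achieving or maintaining an EASI50 score after 8 weeks of treatment will be terminated from the trial".

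Elsewhere the maintenance rule is stated in terms of EASI-50:

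- Protocol Synopsis, Study Design: "those patients not maintaining an EASI-50 response following re-randomization at Week 24, 32, 40 or 48" go to the Escape Arm.
- Protocol Section 3: "those patients not maintaining an EASI-50 response following re-randomization at Week 24, 32, 40 or 48 will be assigned to an Escape Arm".
- SAP 5.1.3.2 names, among those assigned to escape, "patients received topical or systemic rescue therapy between baseline to Week 16 and those patients not maintaining an EASI-50 response".
- SAP Table KGAB.6.1 (Section 6.1.1) defines the Week 24-48 escape population as patients who "escaped to Lebrikizumab 250 mg Q2W due to EASI-50 non-response at Week 24, 32, 40 or 48".
- SAP 6.1.3, 6.1.3.3 and 6.14.1 likewise describe escape as following EASI-50 non-response.

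Table 3 of the protocol gives the timing: "Patients entering Escape Arm at Week 24, 32, 40 and 48". Protocol Section 8.2.2 describes EASI as having "scores ranging from 0 to 72, with the higher values indicating more severe and/or extensive disease".

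On a related matter, Protocol Section 6.1 requires study drug to be stopped permanently if systemic corticosteroids are used for AD. Section 6.3 names oral corticosteroids as an example of systemic rescue in induction. It requires study drug to be stopped, but then allows the patient into the Escape Arm after a washout of at least 5 half-lives.

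**The concern.** The parenthesis is a decision threshold in the protocol section on escape eligibility, and it is the only cut-off that section gives for entry from maintenance. The correctly directed EASI-50 wording further down governs a different decision: termination after 8 weeks in the Escape Arm.

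A site looking for the rule at the escape visits gets no help from the visit instructions. Sections 7.12, 7.14, 7.16 and 7.18 (Weeks 24, 32, 40 and 48) list EASI but no escape check. Protocol 5.3 and SAP 5.3 describe the electronic system's role in the Week 16 re-randomisation only, and the documents do not say what check applies later.

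Applied literally, the parenthesis would do two things:

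- Move patients who are still responding to open-label lebrikizumab. Under the maintenance primary estimand (SAP 6.2.2.1 and the first row of Table KGAB.6.4), transfer to escape is a treatment failure with the value set to baseline, so a responder would be scored as a failure.
- Keep patients who have relapsed, including those on placebo, in their blinded arm without the retreatment that the design intends.

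**Working it through.** **Inputs**

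- Percentage change = 100 × (score − baseline) / baseline (SAP Table KGAB.6.11).
- EASI-50 response: percentage change ≤ −50 (same table).
- Loss of EASI-50: percentage change > −50 (same table).
- Parenthesis in Protocol 5.3.3: score < 0.50 × baseline.
- Eligible baseline: 16 (inclusion criterion 3) to 72 (top of the scale, Protocol 8.2.2).
- EASI route into maintenance: EASI-75, i.e. score ≤ 0.25 × baseline (Protocol 5.3.2).

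**Conversion**

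Score < 0.50 × baseline gives a percentage change below −50, so EASI-50 is met. Loss of EASI-50 gives score > 0.50 × baseline. The two conditions cannot both be true.

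| Baseline | Half of baseline | Parenthesis selects | Loss of EASI-50 selects | EASI-75 bound |
|---|---|---|---|---|
| 16 | 0.5 × 16 = 8 | below 8 | above 8 | 0.25 × 16 = 4 |
| 30 | 0.5 × 30 = 15 | below 15 | above 15 | 0.25 × 30 = 7.5 |
| 72 | 0.5 × 72 = 36 | below 36 | above 36 | 0.25 × 72 = 18 |

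**Individual patients, baseline 30**

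| Score | Change | EASI-50 response | Loss of EASI-50 | Meets parenthesis |
|---|---|---|---|---|
| 3 | −90% | yes | no | yes |
| 7.5 | −75% | yes | no | yes |
| 14.7 | −51% | yes | no | yes |
| 15 | −50% | yes | no | no |
| 15.3 | −49% | no | yes | no |
| 18 | −40% | no | yes | no |
| 30 | 0% | no | yes | no |

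The two rules give opposite answers in every row except exactly 50% of baseline, where neither is met. Baselines of 16 and 72 show the same pattern. Every patient still at EASI-75 meets the parenthesis and none meets the loss rule. A patient back at baseline severity does not meet the parenthesis.

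**The corticosteroid instruction, by section**

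| Section | Rule |
|---|---|
| Protocol 6.1 | Systemic corticosteroids for AD: stop study drug permanently |
| Protocol 6.3, induction | Systemic rescue: stop study drug, continue visits to Week 16, Escape Arm possible after washout of at least 5 half-lives |
| Protocol 5.3.3 | Repeats the washout before Escape Arm treatment |
| Protocol 6.3, maintenance and Escape Arm | Short-term systemic treatment judged case by case with the Medical Monitor |
| Protocol 8.7.2 | Stop study drug for systemic rescue under 6.3; no Early Termination visit for these patients |
| SAP 5.1.3.2 | Systemic rescue in induction is a route to the Escape Arm |

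Escape Arm treatment is lebrikizumab, so a permanent stop in 6.1 cannot stand beside 6.3, 5.3.3 and SAP 5.1.3.2.

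**The case against.** The strongest reply is that nobody would be misled. The main clause of the sentence speaks of failing to maintain response, and the parenthesis cannot be applied without negating it. The Synopsis and Section 3 state the rule correctly, with visit weeks, and the SAP agrees throughout. Literal use would make every patient still at EASI-75 eligible for escape, a result absurd enough that sustained misuse is unlikely. Escape loading doses are also blinded and depend on prior assignment, so some central step presumably stands between a site's judgement and dosing. On this view the point is editorial.

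Most of that is fair. The intent can be recovered, and nothing shows that the inverted rule was programmed or used. The central step, however, is an inference, because the documents do not describe it for Weeks 24 to 48. A wrong number in the section on eligibility is more than a slip of style.

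Two qualifications also stand. Scoring escape as failure holds for the maintenance primary estimand, but not for the supportive estimand for continuous endpoints (SAP 6.2.2.4), which handles transfer hypothetically. On corticosteroids, Section 6.1 ends by pointing to 6.3, and Section 8.7.2 defers to 6.3. Neither removes the permanent stop in 6.1.

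**Conclusion.** The concern holds. The parenthesis in Protocol 5.3.3 is inverted at every eligible baseline from 16 to 72. It contradicts its own sentence and the seven other statements of the maintenance escape rule: Synopsis, Protocol 3, SAP 5.1.3.2, Table KGAB.6.1, 6.1.3, 6.1.3.3 and 6.14.1.

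This is an error of wording in an operative rule. It is not a flaw in the analysis: the SAP definitions are right and no planned analysis uses the inverted cut-off. The practical effect is zero if sites follow the Synopsis and Section 3. It becomes real only where a site applies 5.3.3 literally and nothing downstream stops it, and the documents do not settle how likely that is. It should be corrected. The conflict between 6.1 and 6.3 is a smaller, separate inconsistency affecting the same arm.

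**What to change.** In Protocol 5.3.3, replace the parenthesis with: *(have an EASI score >50% of baseline, i.e., <50% reduction from Baseline, at Week 24, 32, 40 or 48)*. This matches the SAP definition of loss of EASI-50 exactly, including at the 50% boundary, and adds the visits already given in Table 3. Confirm once that the escape logic and site training material use this direction.

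In Section 6.1, make the corticosteroid sentence defer to Section 6.3 for each period:

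- **Induction:** study drug stopped through Week 16, with Escape Arm eligibility after a washout of at least 5 half-lives.
- **Maintenance Period and Escape Arm:** short-term systemic treatment discussed with the Medical Monitor before it starts and judged case by case.
- **Escape Arm:** need for long-term systemic treatment leads to discontinuation from the study.

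Read Section 8.7.2 against the new sentence at the same time.

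The cost is a few words in 5.3.3 and one sentence in 6.1, by amendment or clarification letter, plus the check of logic and training. The SAP needs no change.
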